All patients will be randomized to either a cohort managed with a decision aid (Cohort I) or to a cohort managed without a decision aid (Cohort II). A research fellow does the randomization after the first consult at the outpatient clinic with a computer generated simple randomization sequence.

V. STUDY PROCEDURES

This study will employ a randomized, prospective design. The baseline data are gathered at enrollment. The patients will be randomly assigned to two different cohorts after the encounter with the physician. The physician will be informed that the patient is participating in this study, but will not know to which cohort the patient will be randomized.

Cohort I will be managed with standard care plus a decision aid (henceforth “DA”), and cohort II will be managed without one. The patients in Cohort I will receive the DA, which they can complete in a separate room and take home. The decision aids include information on the disease/condition, treatment options, benefits, risks, scientific uncertainties, and probabilities of potential outcomes tailored to the patient’s health risks factors. Additionally, it includes values clarifications such as describing outcomes in functional terms, asking patients to consider which benefits and risks matter most to them, and guidance in the steps of decision making and

discussing their decision with family/friends. It is interactive and dynamic, helping patients clarify their preferences and come to a decision that feels best to them.

Cohort II will receive the standard care including—at the surgeon’s discretion—the American Society of Surgery of the Hand (ASSH) informational brochure. The patients will have the opportunity to read the brochure in a separate, quiet room or take it home. The ASSH - brochure contains anatomic illustrations of the injury and a discussion of surgical and non-surgical treatments for the diseases, and a general description of expected outcomes. Similar to the patients in cohort II, the patients in cohort I can read and complete the DA in a separate quiet room and take the decision aid home.

After randomization all patients will complete the REDCap questionnaires about the conflict in decision-making, which will take approximately 20 minutes. After completing the study procedures, the physician will return to the room and continue with the visit with the patient. The visit will be timed by a member of the study staff.

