Outcome: Measured variables at enrollment – with REDCap, which will take approximately 20 minutes to fill out:

Demographic Questionnaire:

- Age
- Sex
- Ethnicity
- Race
- Marital status
- Education
- Current work status
- Current or previous occupation
- Hand dominance

Primary outcome:

- Decision conflict scale (DCS) – quantifies the state of uncertainty about a course of action.
- 11-point ordinal satisfaction scale – quantifies the satisfaction with overall treatment.
- 11-point ordinal satisfaction scale – quantifies the satisfaction with decision-making.

Secondary outcome

- Knowledge questionnaire
- Stage of decision making
- Decision Self-efficacy Scale
- Acceptability (Cohort 1 will not receive this questionnaire)
- Pain Self efficacy Questionnaire (PSEQ)
- 9-item Shared Decision Making Questionnaire (SDM-Q-9)

Primary health outcomes variables:

- Quick-DASH
- EQ-5D

At follow-up 1 week-1 month and 6 months after enrollment we will have patients complete the following online REDCap questionnaires, which will take approximately 20 minutes:

The decision-making process variables:

- Quick-DASH
- PROMIS Upper Extremity CAT
- DCS
- 11-point ordinal satisfaction scale – quantifies the satisfaction with overall treatment and decision-making.

- 11-point ordinal satisfaction scale – quantifies the satisfaction with decision-making.
- Decision Regret scale (measures distress or remorse after a health care decision)

VI. BIOSTATISTICAL ANALYSIS

Statistical issues

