Based on previous studies, scores of 25 or lower on the DCS (0-100) are associated with low decisional conflict and following-through with decisions.¹⁵ On the other hand, scores of 39 or higher are associated with heightened mental conflict resulting in a delay in the decision making.¹⁵ Our study will measure the rate of patients having a conflict in decision-making. A sample size of 126 total patients was chosen to measure our primary outcome with 80% power, 0.5 effect size and an alpha of 0.05. Chi-square tests will be conducted to determine the differences between two categorical variables. Independent Student's t-tests will be performed to determine the differences between continuous and dichotomous variables. Paired samples T-test will be used to compare the mean scores for the same group on different occasions. Pearson's correlation or Spearman correlation will be used to explore the strength of the relationship between the conflict of decision-making and the use of decision aids. Wherever the minimum expected cell frequency is less than five, the Fisher's exact test will be used instead of the Pearson's Chi-square test. All variables with significant ($p < 0.05$) or near significant ($p < 0.08$) relationships will be evaluated with backwards multivariate/binary logistic regression (depending on the outcome variable) Descriptive statistics will be summarized in terms of means, standard deviations or frequencies, and will be calculated at each time point. Incomplete data will be adequately described and mean imputation will be used when deemed necessary. We will use IBM SPSS ® (19) to perform the data analysis.

VII. RISKS AND DISCOMFORTS (Stratify by common and uncommon)

The greatest discomfort associated with participation is the time required to fill out the decision aid and complete the questionnaires. Completing the DA will require approximately 20

minutes, but this can be done at home. The Questionnaires will require approximately 20 minutes at the time of enrollment.

VIII. POTENTIAL BENEFITS

Individuals managed without a DA will not experience any additional benefits, but will also not have any extra risks. Patients managed with a DA, on the other hand, may experience less decisional conflict and improved knowledge about their disease. The study will benefit society as a whole by providing a better understanding of the factors that influence patient decision-making and surgical outcomes for orthopedic problems.

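### The enrollment questionnaires appear to be completed after randomization, and the plan has no pre-randomization score on the Decision Conflict Scale

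*Combined protocol and SAP*

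**What the plan says.** Section V (Study Procedures) first states: "The baseline data are gathered at enrollment". The next sentence reads: "The patients will be randomly assigned to two different cohorts after the encounter with the physician". After describing the decision aid (DA) and the brochure, the section continues: "After randomization all patients will complete the REDCap questionnaires about the conflict in decision-making, which will take approximately 20 minutes".

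The enrollment variables then follow as a single list, introduced by: "Outcome: Measured variables at enrollment – with REDCap, which will take approximately 20 minutes to fill out". The list holds demographics, the DCS, two satisfaction scales, knowledge, stage of decision making, decision self-efficacy, Acceptability, PSEQ, SDM-Q-9, Quick-DASH and EQ-5D. One entry depends on the assigned arm: "Acceptability (Cohort 1 will not receive this questionnaire".

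Section VII (Risks and Discomforts) repeats the time: "The Questionnaires will require approximately 20 minutes at the time of enrollment". It also allows the DA to be completed at home.

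At the two follow-ups (1 week to 1 month, and 6 months), the DCS and Quick-DASH are repeated. EQ-5D and PSEQ are not listed there.

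Section VI (Biostatistical Analysis) plans independent t-tests and chi-square tests between groups, and paired t-tests within a group across occasions. It also plans a backward regression on every variable that reaches p < 0.05 or p < 0.08. It specifies no adjustment for a baseline value.

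**The concern.** A measurement can serve as a baseline only if it precedes assignment, or at least exposure to the intervention. Here the first DCS comes after assignment, when Cohort I may already have read the DA. Three things follow.

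- A paired comparison of DCS from enrollment to follow-up would start from a score that may already contain part of the DA effect. In Cohort I it would then understate the change.
- The regression screen has no rule that keeps out variables measured after randomization. An enrollment score that the DA can influence, such as PSEQ or knowledge, could be adjusted for as though it were a baseline characteristic. That can distort the estimated DA effect.
- A pre-randomization score on the same instrument is usually the strongest available predictor of the outcome. The plan has none, so the primary comparison forgoes the precision it would bring.

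**Working it through.** **Timing, from the text**

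1. The post-randomization sentence in Section V covers the questionnaires on decisional conflict. The list defines the DCS thus: "Decision conflict scale (DCS) – quantifies the state of uncertainty about a course of action". Its only other listed times are the two follow-ups. So no pre-randomization DCS is specified, and this holds on any reading.
2. For the rest of the battery, three facts point to one session after assignment. There is one undivided list. Sections V (twice) and VII all give about 20 minutes. Acceptability can be given or withheld only once the arm is known.
3. Against this, the post-randomization sentence does not name Quick-DASH, EQ-5D, PSEQ or demographics, and Section V speaks of baseline data just before it describes assignment. Post-randomization timing of these forms is therefore a well-supported inference and is not stated.
4. Exposure at the time of the battery is not fixed, because the DA may be read in a separate room or taken home.

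**The plan's sample size**

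Inputs from Section VI: effect size 0.5, alpha 0.05, power 80%, total 126. Assumed: two-sided test and 1:1 allocation.

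- n per arm = 2 × (1.960 + 0.842)² / 0.5² = 62.8, so 63 per arm and 126 in total. The stated figure is reproduced.
- Power at 63 per arm = Φ(0.5 × √(63/2) − 1.96) = Φ(2.806 − 1.96) = 80.1%. The exact t-test gives 79.5%.

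This calculation compares two means with no covariate, so it does not depend on a baseline DCS.

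**Gain from a pre-randomization DCS**

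Adjusting for a covariate that correlates r with the outcome multiplies the residual variance by 1 − r². At 63 per arm:

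Power = Φ(2.806 / √(1 − r²) − 1.96)

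| Assumed r | √(1 − r²) | Power |
|---|---|---|
| 0 | 1 | 80% |
| 0.4 | 0.917 | 86% |
| 0.5 | 0.866 | 90% |
| 0.6 | 0.800 | 94% |

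Over a wider range, r = 0.3 gives 83.7% and r = 0.7 gives 97.6%. The documents give no r. The formula applies to DCS as a continuous score.

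**Change measured from a post-randomization DCS**

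Suppose a fraction f of a 0.5 SD effect is already present at enrollment. Change from that score then captures only 0.5 × (1 − f) SD of it: 0.375, 0.25 or 0.125 SD for f = 25%, 50% or 75%. If the arms were compared on that change, with r = 0.5 between occasions (so the SD of change is √(2 × 0.5) = 1), power at 63 per arm would be 55.8%, 28.9% or 10.4%, against 80.1% from an unexposed start. Both f and r are assumptions. The plan does not name this between-arm comparison of change, so these figures only illustrate how much of the effect a late starting point can hide.

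**The case against.** The strongest reply is that randomization already protects the primary comparison. The between-group tests in Section VI are unadjusted. Both arms complete the DCS after assignment, so the contrast is valid without a baseline, and the 126 was derived without one. The paired tests are within-group and are not the DA contrast. All of this stands, and it makes the missing DCS a matter of precision and interpretation.

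A reader might infer more: that Quick-DASH, EQ-5D and PSEQ are shown to be contaminated baselines, or that the DA effect on DCS is biased. The documents do not support either. No section places those three forms before or after assignment, and reading the DA first is not guaranteed. Section V lists all three as outcomes, and measuring an outcome after randomization is not a fault. A same-day effect on Quick-DASH is unlikely in any case. Bias from adjustment could arise only through the loosely worded backward regression. Its size cannot be derived, because the documents give neither the DA effect on such a score nor that score's relation to DCS.

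It can also be objected that moving the whole battery ahead of randomization would do harm. That is right for PSEQ and EQ-5D. Enrollment is their only listed measurement, so moving them would leave no post-randomization value to compare.

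**Conclusion.** The point holds in a limited form. The plan specifies no pre-randomization DCS, and its single enrollment battery appears to be completed after assignment. The unadjusted between-arm comparison of post-randomization DCS is valid, and N = 126 stands.

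Three things are affected: the meaning of paired DCS changes from enrollment, the status of enrollment scores in the regression, and precision. On precision, adding a pre-randomization DCS would take power at 126 patients from 80% to about 86–94%. That figure assumes a correlation of 0.4–0.6, two-sided alpha, 1:1 allocation and a continuous DCS. Section VI also speaks of measuring the rate of patients with decisional conflict, and the gain does not carry over as calculated to a dichotomized endpoint.

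The timing of Quick-DASH, EQ-5D and PSEQ is an ambiguity for the protocol to resolve. It is not a demonstrated error.

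**What to change.** 1. State in Section V which forms are completed before randomization and which after.
2. Complete demographics and Quick-DASH before randomization. Quick-DASH is repeated at both follow-ups, so no outcome is lost.
3. Take the DCS once before randomization, after the first consult. Analyse DCS as a continuous score and adjust the between-arm comparison for that value.
4. Keep the existing DCS, knowledge, stage of decision making, decision self-efficacy, satisfaction, SDM-Q-9 and Acceptability after randomization. State their timing relative to reading the DA, given that it may be taken home.
5. Leave PSEQ and EQ-5D after randomization if they are to remain outcomes, since neither is repeated at follow-up.
6. Add to Section VI that no score measured after randomization is used as a covariate for the DA effect.

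Cost: moving demographics and Quick-DASH only reorders existing forms. The extra DCS takes a few minutes. It may also sensitize patients to the questions, and that effect may differ between arms because the DA itself works by clarifying values. The protocol should acknowledge this.

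### As the enrollment visit is sequenced, SDM-Q-9 comes before the physician returns and is never repeated, so it cannot capture a decision-aid effect on the later discussion

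*Combined protocol and SAP*

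**What the plan says.** The protocol fixes the order of the enrollment visit in two places. Section IV (Subject Enrollment) states: "A research fellow does the randomization after the first consult at the outpatient clinic with a computer generated simple randomization sequence". Section V (Study Procedures) repeats the point: "The patients will be randomly assigned to two different cohorts after the encounter with the physician". Cohort I then receives the DA, and Cohort II receives standard care with a brochure if the surgeon chooses. Next, "After randomization all patients will complete the REDCap questionnaires about the conflict in decision-making, which will take approximately 20 minutes". The same part of Section V ends the sequence with "After completing the study procedures, the physician will return to the room and continue with the visit with the patient".

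The outcome list in Section V is headed "Measured variables at enrollment – with REDCap, which will take approximately 20 minutes to fill out". SDM-Q-9, the 9-item shared decision making questionnaire, is one of six secondary outcomes under that heading. The later list is introduced by "At follow-up 1 week-1 month and 6 months after enrollment we will have patients complete the following online REDCap questionnaires". It contains Quick-DASH, PROMIS Upper Extremity CAT, DCS, the satisfaction scales and Decision Regret. SDM-Q-9 is not in it.

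Section VII (Risks and Discomforts) describes the same burden once more: "The Questionnaires will require approximately 20 minutes at the time of enrollment". No section describes a questionnaire session on that day after the physician has come back.

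**The concern.** A DA can change how a patient and physician share a decision only in a conversation that follows it. Section I gives this as part of the rationale, reporting that such tools prepare patients for meeting their physician. In this plan, that conversation is the resumed part of the visit. The one instrument named for shared decision making appears to be completed before it and is not given again.

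Section II includes communication among the domains in which the cohorts are to be compared. If SDM-Q-9 is reported as evidence on that domain, either result invites a wrong conclusion. No difference could be read as the DA having no effect on shared decision making, although the relevant discussion was never rated. A difference could be read as better sharing, although the rated consult was over before anyone was assigned.

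**Working it through.** The point concerns order of events, so the check sets the statements side by side. The plan gives no figure for SDM-Q-9.

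**Step 1: the sequence in Sections IV and V.**

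| Order | Event | Could the DA influence it? |
|---|---|---|
| 1 | Encounter with the physician | No, it precedes assignment |
| 2 | Randomization | – |
| 3 | DA, or standard care with optional brochure | – |
| 4 | REDCap questionnaires, about 20 minutes | Yes, as the patient's answers |
| 5 | Physician returns and the visit continues | Yes |

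The text puts the questionnaires after randomization. It does not require the DA to be finished first, since the DA may be taken home.

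**Step 2: where SDM-Q-9 falls.** Section V, describing the visit, mentions questionnaires on decisional conflict and does not name SDM-Q-9. The outcome list puts SDM-Q-9 in the enrollment battery. The visit description, the outcome list and Section VII each give about 20 minutes for questionnaires at enrollment, and no other session that day is described. The natural reading is a single battery at row 4.

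**Step 3: the alternative placement.** Section V also says that baseline data are gathered at enrollment. If SDM-Q-9 were taken before randomization, it would be a pure baseline measure and could show no DA effect of any kind. If it is meant to follow row 5, the text does not say so. The plan needs a correction under each reading.

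**Step 4: what a difference between cohorts could contain.** Assume that SDM-Q-9 rates the consultation. At row 4, a difference in scores has two possible sources besides chance:

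- *Sharing that took place in the first encounter.* The DA cannot have altered this. Randomization came later, and Section V says that the physician does not know the cohort to which the patient will be randomized.
- *How the patient judges that encounter afterwards.* Cohort I patients have been handed material on options, risks and values, and they know it. This may shift their view of the earlier consult in either direction. The documents give no basis for its size.

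Sharing in row 5 is not a component of the score, because it has not yet happened.

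**Step 5: reach of the problem.** Section VI sizes the trial on the primary outcome with effect size 0.5, 80% power and alpha 0.05. Taking a two-sided test, 1:1 allocation and a standardized mean difference, n per arm = 2 × (1.96 + 0.842)² / 0.5² = 62.8, rounded up to 63, or 126 in total. This reproduces the stated 126. SDM-Q-9 does not enter the calculation, so changing its timing leaves the sample size as it is.

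**The case against.** Five points can fairly be made on the other side.

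- *The placement is inferred.* This stands as a caveat. The inference is strong, for the reasons in steps 2 and 3 of the working, but the sponsor may have intended something else.
- *The documents do not give the SDM-Q-9 items or the encounter they refer to.* This also stands. That the form rates the consultation is taken from its name and purpose.
- *The score may still differ between cohorts.* A reader might infer that the expected difference is zero by design, and that a test would reject in about 5% of trials whatever the DA does. The documents do not support that. It would require identical score distributions in both cohorts. The patients are not blinded, and those in Cohort I answer after receiving the DA, so re-appraisal of the first consult could separate the scores. The defect is that the result cannot be interpreted as an effect on sharing. A null is not guaranteed.
- *The importance is limited.* SDM-Q-9 is one of six secondary outcomes and is in none of the hypotheses in Section II, which concern decisional conflict, satisfaction, clinical outcomes and regret. No section formally assigns it to the communication domain. This is correct and keeps the point modest.
- *Later measures of the decision process exist.* DCS and satisfaction with decision-making are repeated at follow-up, so the plan does have process measures taken after the resumed visit. Neither is the instrument named for shared decision making, so the gap for SDM-Q-9 remains.

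**Conclusion.** The concern holds for SDM-Q-9. Followed as written, the plan collects it before the only same-day physician contact that the DA could influence, and does not collect it again. It cannot measure a DA effect on sharing in the resumed discussion. A difference between cohorts would reflect a changed view of a consult held before randomization, and a null would be silent on the resumed visit.

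This rests on two assumptions: that SDM-Q-9 belongs to the single enrollment battery completed before the physician returns, and that it rates the consultation with the physician. The size of any re-appraisal effect cannot be derived from the documents, so no rejection rate or expected difference is claimed.

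One secondary outcome is affected. A reader might extend the criticism to the trial's decision-process results as a whole. The documents do not support that, since DCS and the satisfaction items are repeated at follow-up and the primary hypothesis does not depend on SDM-Q-9.

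**What to change.** Give SDM-Q-9 at the end of the enrollment visit, after the physician has returned, or as the first form in the 1 week-1 month online follow-up. State in Section V when it is given and which encounter the patient is asked to rate. Leave DCS, the knowledge questionnaire and the satisfaction items where they are; the satisfaction items are already repeated at follow-up.

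This is a reordering of REDCap forms, with no new instrument, no new visit and no change in sample size. Each option has a cost:

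- *End of visit:* a few more minutes for the patient. Patients who complete the DA at home may not have used it by then, so for them the form may still precede exposure.
- *First follow-up:* some non-response, and recall that varies across a window of 1 week to 1 month.

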We plan a prospective randomized controlled study with a null hypothesis that patients randomized to a newly developed decision aid in addition to usual care have no difference in decisional conflict compared to patients treated with usual care and the ASSH brochures.

Secondary Null Hypotheses:

Our second aim is to determine if decision aids influence patient satisfaction, clinical outcomes and regret. To address this second aim, we will test the null hypothesis, which is that there is no difference in the rate of satisfaction, clinical outcomes and regret between patients treated with and without a decision aid.

III. SUBJECT SELECTION

Participants will be recruited among patients presenting to Orthopedic Hand Service of Massachusetts General Hospital with moderate or severe TMC arthrosis or CTS or CTD or DRF and or TF. The study physician will confirm the diagnosis and introduce the study to the patient. Each participant following the explanations by the interventionist will sign a detailed consent form at the time of their baseline diagnostic assessment. The consent form will include all of the study procedures, information about potential risks and benefits of participation, and information regarding who they can contact for further questions. It also will state that participation is voluntary, that participants can refuse to answer any question, and that they can withdraw from the study at any time, and that study participation is in no way related to their care. For follow-up, participants may be contacted by mail, phone and email.

Inclusion criteria:

All adult (>18years old) English-speaking patients presenting to one of the participating hand surgeons, [name], [name], [name] and [name] from the Massachusetts General Hospital with moderate or severe TMC arthrosis, CTS, CTD, DRF and TF will be invited to enroll.

Exclusion criteria include:

1. Patients with prior operative treatment or corticosteroid injection for TMC, CTS, CTD, DRF and TF on the same limb.
2. Patients that have previously used the Decision Aids

IV. SUBJECT ENROLLMENT

The study will be described in detail and the treating physician/study staff will obtain informed consent. Patients will be given a copy of the consent form and be informed that their participation is voluntary and that they may refuse at anytime. The enrolling physician will emphasize that participation is voluntary.

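### Section II makes decisional conflict the only primary hypothesis, but Section V lists it with two satisfaction scales as primary outcomes and gives no multiplicity rule; if any one may count as success, the false-positive chance is about 8% to 14%, not 5%.

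*Combined protocol and SAP*

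**What the plan says.** - **Section II, Primary Null Hypothesis.** There is one: patients given the decision aid "have no difference in decisional conflict compared to patients treated with usual care and the ASSH brochures".
- **Section II, Secondary Null Hypotheses.** Satisfaction is placed here: "Our second aim is to determine if decision aids influence patient satisfaction, clinical outcomes and regret".
- **Section V, Primary outcome.** Three items are listed: the DCS, an "11-point ordinal satisfaction scale – quantifies the satisfaction with overall treatment", and a second 11-point scale for satisfaction with decision-making. A separate secondary outcome list follows. Below that, a further heading labels Quick-DASH and EQ-5D as primary health outcome variables.
- **Section V, timing.** "After randomization all patients will complete the REDCap questionnaires about the conflict in decision-making". The DCS and the satisfaction scales are repeated at follow-up.
- **Section VI, sample size.** The total of 126 "was chosen to measure our primary outcome with 80% power, 0.5 effect size and an alpha of 0.05". Just before this, the section says: "Our study will measure the rate of patients having a conflict in decision-making".

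The document contains no order of testing, no division of alpha, and no statement of how many of the listed primary outcomes must be significant. The only other significance thresholds in Section VI, 0.05 and 0.08, select variables for regression models.

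**The concern.** The two sections disagree on what decides the trial. The satisfaction scales are secondary in Section II and primary in Section V, and neither section is given precedence. The error rate and the power depend on which is followed:

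- If Section II governs, the primary test has a 5% error rate.
- If Section V governs and any one of the three suffices, the error rate exceeds 5%.
- If Section V governs and all three are needed, the error rate does not rise, but power falls below the planned 80%.

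Because the rule is open, it could be settled after the results are known. This matters in practice. The background section calls the evidence on satisfaction inconclusive (of eleven trials, four found higher satisfaction and seven no significant difference), while it describes reduced decisional conflict as shown in other fields. If the DCS and satisfaction diverge in this trial, the two sections would give different answers on whether the primary outcome was met.

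**Working it through.** **Inputs from the plan.** Section VI gives alpha 0.05, power 80%, effect size 0.5 and N = 126. Section V gives three listed primary outcomes.

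**Assumptions.** Tests are two-sided, because the null is one of no difference. Allocation is 1:1, because simple randomization to two cohorts is described without a ratio. The effect size is read as a standardised mean difference d. Correlations between the test statistics are not given, so a range is used, with the same correlation r for every pair.

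**Step 1: reproduce N = 126.** Normal approximation:

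n per arm = 2 × (1.960 + 0.842)² / 0.5² = 62.8, rounded up to 63, so 126 in total.

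This matches. The two-sample t test has 79.5% power at 63 per arm. A one-sided test would give 100 in total, so the two-sided reading fits. The calculation is for one comparison, with no allowance for further primary tests.

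**Step 2: any one of three suffices, each at two-sided 0.05.** For independent tests:

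1 − (1 − 0.05)³ = 1 − 0.8574 = 0.1426.

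For correlated tests, one minus the probability that all three statistics lie within ±1.96 was obtained by numerical integration.

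| Common correlation r | Chance of at least one false positive |
|---|---|
| 0 | 14.3% |
| 0.3 | 13.6% |
| 0.5 | 12.5% |
| 0.7 | 10.9% |
| 0.8 | 9.8% |
| 0.9 | 8.4% |
| 1 | 5.0% |

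**Step 3: all three required.** Take 63 per arm and d = 0.5 on each outcome. The expected test statistic is 0.5 × √(63/2) = 2.806, so power for one outcome is 80.1% (normal approximation). If independent, power for all three is about 0.801³ = 0.51. By integration it is 61% at r = 0.5, 66% at r = 0.7 and 72% at r = 0.9.

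**Step 4: keep three equal primaries with Bonferroni.** Alpha per test is 0.05/3 = 0.0167.

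- Power per outcome at 126 patients falls to 66.0% (normal approximation).
- For 80% power on each outcome, the normal approximation gives 2 × (2.394 + 0.842)² / 0.25 = 83.8, so 84 per arm and 168 in total, against 126 at alpha 0.05.
- The t test gives 85.2, so 86 per arm and 172 in total, against 64 per arm and 128 in total at alpha 0.05.

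**Step 5: form of the DCS outcome.** The figures 0.5 and 126 fit a comparison of mean scores. An effect of 0.5 on the arcsine scale for two proportions (Cohen's h) also gives 62.8 per arm, so the sample size alone does not show whether a mean or a rate is meant. Section VI mentions a rate but gives no control rate and does not say which of its two DCS thresholds defines conflict.

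**The case against.** The strongest counter-argument is that the documents lean towards a single primary. Section II is explicit, Section VI discusses DCS thresholds and then refers to one primary outcome, and the odd one out is a heading over a questionnaire list in Section V. That list also has a heading for primary health outcomes, so the labels may only group instruments. On this view it is a labelling slip, and a later switch would be detectable against Section II. This supports the choice of fix, but it does not remove the contradiction. Section V is where the measured outcomes are defined, it sets a separate secondary list below the primary one, and a report calling satisfaction a primary outcome could cite it accurately.

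A second objection is that 8% to 14% rests on an any-one rule that the plan never states, and on assumed correlations. Both are true. With non-negative correlation the full range is 5% to 14.3%. Independence is unlikely for three self-reports from the same patient at the same sitting, and perfect correlation is equally unlikely for three different scales. The any-one rule is neither stated nor excluded, and that is the defect.

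A third objection is that setting 172 patients against the protocol's 126 mixes a t-test figure with a normal-approximation one. This stands: like for like, the increase is 126 to 168 or 128 to 172. It affects only the cost of an option that is not preferred.

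**Conclusion.** The concern holds. The current text contradicts itself on which outcome or outcomes decide the trial, and nothing in the document resolves it. The error rate is 5% if the DCS alone decides. It is about 8% to 14% if any one of three suffices, for correlations from 0.9 down to 0. If all three are required, power is about 51% to 72%, for correlations from 0 to 0.9 and an assumed d = 0.5 on each outcome. These figures do not count Quick-DASH and EQ-5D under their own primary heading, the repeated follow-up assessments, or the choice between DCS mean and DCS rate. Treating any of these as primary too could raise the any-one error further. This must be corrected, because a rule chosen after the outcome data have been compared cannot restore a prespecified error rate.

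**What to change.** Bring Section V into line with Section II:

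1. Name the DCS as the sole primary outcome, measured at the post-randomization enrollment assessment and tested at two-sided 0.05.
2. State its form. The mean score fits the existing calculation. If the rate of patients with conflict is intended, Section VI needs a cut-off, a control rate and its own power statement.
3. Relabel both satisfaction scales as secondary, and reword the heading over Quick-DASH and EQ-5D to agree with the secondary status of clinical outcomes in Section II.
4. If satisfaction is to be confirmatory, test it in a stated fixed sequence, and only after the DCS is significant. This spends no additional alpha.

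With the mean score as primary, these are wording changes in Sections V and VI, with no new data or patients, and 126 stands. The price is that satisfaction loses its stand-alone primary status.

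If the sponsor wants three equal primaries, the plan needs a stated multiplicity rule and a new sample size. With Bonferroni at 0.0167 and 80% power on each outcome at d = 0.5, that means 168 patients by the normal approximation that reproduces 126, or 172 by the t test.
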